1. Self-report of significant incontinence in the 6 months prior to prostatectomy. Based on data from the Prostate Cancer Outcomes Study,² we would expect about 14% of potential participants to have any pre-existing incontinence, 10% with minor leakage. In our pilot study of a clinic-based intervention at the Birmingham VAMC (Preliminary studies Section - Study #5), 2 of 30 men scheduled for prostatectomy (7%) had minor incontinence prior to prostatectomy and none of them had severe incontinence. In our prior clinical trial of preoperative pelvic floor muscle training for men undergoing radical prostatectomy, we operationalized this exclusion as “no more than 2 incontinence episodes in the last 6 months, not including post-void dribbling” and will do the same for the current proposal.⁴ Men who are excluded will be offered referral to the VA Continence Clinic for perioperative rehabilitation.

Sample size

Given the primary outcome is time to event, survival analyses will be used to conduct the analyses. A one-sided log rank test with an overall sample size of 156 subjects (of which 78 are randomized to standard care and 78 are randomized to Telehealth) achieves 80% power using a one-tailed 0.05 significance level to detect a difference of 0.2000 between 0.55 and 0.35 - the proportions remaining incontinent in the two groups surviving in standard care and Telehealth respectively. This effect corresponds to a hazard ratio of 1.756. These results are based on the assumption that the hazard rates are proportional. The proposed effect size is based on our earlier research.⁴ Power and sample size has been calculated using the Log-Rank procedures within PASS 11.0 (Hintze, J. (2011). PASS 11. NCSS, LLC. Kaysville, Utah, USA. www.ncss.com).

In our pilot study, after randomization, 10% of Veterans decided to have radiation instead of radical prostatectomy or were found to have positive lymph nodes during surgery and their prostatectomy aborted. These men ended participation in the study because they no longer had the risk factor for incontinence. To recruit sufficient numbers of Veterans so that we obtain the full 156 subjects indicated by our power calculation above, we will plan to randomize 10% more Veterans for a total of 172. When we reach the total of 156 Veterans having had a radical prostatectomy, we will end recruitment.

Recruitment Procedures at the VAMC

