Intensive protocol training will be done for the project managers at both sites as well as for the nurse interventionist. This will occur on-site for both the Atlanta and Birmingham sites, and then be supplemented by weekly VANTS calls to prevent procedure drift and discuss problems as they arise, The PI is also available any time by cell phone to answer more urgent questions. On the weekly calls, we will review results of the interventions by the study coordinators for participants who are non-adherent to conducting their daily telehealth sessions. The nurse interventionist in Birmingham will be conducting all telephone interventions for participants at all sites who are completing their telehealth session, but not meeting learning goals. A formal monthly meeting will be conducted with the PI and nurse interventionist to review all telephone support, including content and results. Because the nurse interventionist's and the PI's offices are close together in the Birmingham office of the GRECC, we also anticipate being able to discuss these calls immediately after they occur as well.

Follow-Up

After completing the daily 2-month post-operative program, participants will complete an outcome assessment once a week until 6 months after their surgery, and then again at 9 and 12 months. Weekly, this will be the ICIQ-UI short form, and every 4 weeks the EPIC-UI and the EPI, GPI, and PSQ will be added as outlined in **Table 4**. Specifics for these measures are in the following section on Outcome Measures. For the 9- and 12-month outcomes assessment, a questionnaire will be mailed with a post-paid, pre-addressed envelope only if the patient does not respond to the telehealth session. If participants in either group do not do a weekly assessment, they will be called to prompt them to complete the assessment or offered the opportunity to complete it on the telephone.

Table 4 – Data Collection Schedule						
	Pre-op Visit	1 Month After Discharge	Ongoing in the 6-Month Post-op period	At 6 Months Post-op	At 9 Months Post-op	At 12 Months Post-op
CPRS Abstraction	H & P	Hospital Record				CPRS Clinic Notes and Medication Profile
Continence History	X					
ICIQ-UI-SF [4 items]	X		WEEKLY via telehealth program	X	X	X
EPIC-UI [4 items]	X		MONTHLY via telehealth program	X	X	X
IIQ-SF, IPSS QoL question, other QoL questions [11 items]	X**		MONTHLY via telehealth program		X	X

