Exercise Adherence Measure [3 items]			MONTHLY via telehealth program - intervention group only	X	X	X
Bladder Control Strategy Adherence [3 items]			MONTHLY via telehealth program - intervention group only	X	X	X
PSQ, EPI, GPI [1 item each]	**		At 2 MONTHS post-op and then MONTHLY via telehealth program	X	X	X

CPRS = Computerized Medical Record System; EPI = Estimated Percent Improvement; EPIC-UI = Expanded Prostate Cancer Index Composite Urinary Incontinence Subscale; GPI = Global Perception of Improvement; H & P = History and Physical; ICIQ-SF = International Consultation on Incontinence Questionnaire – Short Form; IIQ-SF - Incontinence Impact Questionnaire Short Form; IPSS QoL- International Prostate Symptom Score Quality of Life; PSQ = Patient Satisfaction Question
 
**Note that the PSQ, EPI, and GPI are patient global impressions of improvement and satisfaction and cannot be collected at baseline. Same with return to work after surgery and return to usual activities after surgery (other QoL items)
						

Participants who have not achieved continence by 12 months after their surgery will be offered treatment in the GRECC Continence Clinics.

Telehealth Equipment Return

Once the participant has completed the telehealth portion of the study, the study coordinator will check for any upcoming appointments in CPRS. If they have been loaned a tablet, it is optimal to have it returned in person. If no appointments are scheduled in the near future, the participant will be provided with a box and a postage-paid, return mailing label. The participant will be responsible for packaging the tablet in the provided box and dropping it off at the nearest UPS store. If the participant does not wish to deliver the telehealth device to the nearest UPS store or there is not a store nearby, a UPS pick-up at their home will be scheduled with the participant's permission.

Outcome Measures

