5. Participation in social activities outside your house?				
6. Emotional health (nervousness, depression, etc)?				
7. Feeling frustrated?				

IPSS Quality of Life Question.³² Frequently administered with the AUA Symptom Index, this validated quality of life measure has been shown to be sensitive to change after treatment in clinical trials including our own work. It is shown in **Figure 2**.

Figure 2 - IPSS Quality of Life Question: If you were to spend the rest of your life with your urinary problem the way it is now, how would you feel about that? ↑
 Delighted, Pleased, Mostly satisfied, Mixed (about equally satisfied and dissatisfied), Mostly dissatisfied, Unhappy, Terrible

Other Quality of Life Questions: We have supplemented the validated questionnaires with additional quality of life questions in much of our past research.^{4,18-21} These additional data points provide additional information of the impact of incontinence. We plan to ask the participants the following questions each month 1-6 months post-operatively and again at 9 & 12 months post-operatively:

- How disturbing is the urine leakage problem to you? (not at all, somewhat, or extremely disturbing)
- How much does leakage of urine restrict your activities? (not at all, some of the time, most of the time, all of the time).
- Have you been able to return to work since your surgery? (yes, no, retired or disabled)
- Have you been able to resume your usual activities since your surgery? (yes, no)

Exercise Adherence Questionnaire: We will measure adherence to exercises monthly, more frequently as the exercise routine is being established, with a brief questionnaire used in our NIH-funded incontinence research since 1989, including our trial of pelvic floor rehabilitation for post-prostatectomy incontinence,⁴

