Our hypothesis for the secondary outcomes is that total ICIQ-SF, EPIC-UI total Score, Pad use, GPI, EPI, PSQ, IIQ, IPSS QoL, return to work or normal activity, and amount of disturbance caused by incontinence will be better in the pelvic floor muscle rehabilitation group.

Initially, descriptive analyses will be conducted to examine distributions of the frequency of symptoms and possible covariates. Extreme values will be checked for accuracy and recoded as indicated. Transformations may be employed to correct for skewness or heterogeneity as needed.

The ICIQ-SF total score and the EPIC-UI total score will be analyzed using multiple regression analysis to regress the 6 and 12-month scores on treatment group, while controlling for baseline score (first score after catheter removal post-operatively). Pad use will be dichotomized into no pad use and any pad use. Pad use will also be analyzed descriptively as no pads, 1 pad, or 2 or more pads. The chi square statistic and the t test for independent samples will be used. Both measures are necessary for comparison with earlier studies. Multiple regression will be used for the GPI, EPI, and PSQ at 6 and 12 months. There is no baseline for these measures as they are the patients’ evaluations of their improvement and treatment satisfaction. For the IPSS QoL question, questions on activity restriction, disturbance, and return to work or normal activity, the chi square statistic and the t test for independent samples will be used.

Qualitative Analysis

To ensure analytic rigor, the following procedures will be followed: (1) data immersion (reading/listening and re-reading/listening to the text); (2) thematic identification and articulation (discovering, naming, defining codes/variables); (3) data categorization (developing a coding scheme); (4) pattern articulation (identifying connections within and between codes); (5) data interpretation (recognizing how the patterns transcend individual experiences and reflect larger social processes). As an analytical process, content analysis involves sorting and making sense of written and narrative data. The goal is not to generalize across a population, but rather to provide understanding and explanation from the respondent's perspective.

DISSEMINATION PLAN

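### The IPSS quality-of-life comparison leaves a scheduled pre-operative score and the randomisation factors unused: a valid analysis, but a free and minor gain in precision is missed

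*Combined protocol and SAP*

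**What the plan says.** All references are to the combined protocol and SAP.

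- **Planned test** (Data Analysis, Outcome Variables Analysis): "For the IPSS QoL question, questions on activity restriction, disturbance, and return to work or normal activity, the chi square statistic" and the independent-samples t test are to be used. No covariate and no time point is named, and the sentence does not say which test goes with which item.
- **Other scores in the same paragraph:** the ICIQ-SF and EPIC-UI totals at 6 and 12 months are regressed on treatment group "while controlling for baseline score (first score after catheter removal post-operatively"). GPI, EPI and PSQ are also given multiple regression at 6 and 12 months, and the plan explains that they have no baseline. It gives no such reason for the IPSS question.
- **Data collection** (Follow-Up, Table 4): the row "IIQ-SF, IPSS QoL question, other QoL questions [11 items"] is marked at the pre-operative visit with a double-asterisk footnote. The footnote removes PSQ, EPI and GPI from baseline collection and adds: "Same with return to work after surgery and return to usual activities after surgery (other QoL items"). The IPSS question is not among the exemptions.
- **Timing of the other quality-of-life questions** (Secondary Outcome Measures): disturbance, activity restriction, return to work and usual activities are asked "each month 1-6 months post-operatively and again at 9 & 12 months post-operatively". No pre-operative time is listed.
- **Stratification and Randomization:** strata are age (below 65, or 65 and over) and Gleason score (below 7, or 7 and over), with a separate schedule for each site.

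**The concern.** A pre-operative score on the same question is an obvious covariate for a follow-up comparison. Under Recruitment Procedures the baseline assessment is completed before the man gets access to the telehealth program, so the score cannot be affected by the training. If it predicts the later answer, leaving it out makes the standard error larger than necessary and leaves any chance baseline difference between the groups uncorrected. The factors that shaped the randomisation are dropped in the same way.

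Improving quality of life is part of the primary objective in Specific Aims, yet the trial is sized only for time to continence. The IPSS comparison has no stated power, so precision that costs nothing is worth having.

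**Working it through.** **1. The plan's own power figure.** The only one is for the primary log-rank test: 156 men, "of which 78 are randomized to standard care and 78 are randomized to Telehealth", 80% power, one-sided 0.05, with 0.55 and 0.35 remaining incontinent.

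- Hazard ratio = ln(0.35)/ln(0.55) = 1.756, as stated.
- Freedman events = [(2.756/0.756) × (1.645 + 0.842)]², rounded up to 83. With a mean event share of 0.55, N = 83/0.55 = 151 (152 with equal arms).
- At N = 156, expected events are 156 × 0.55 = 85.8 and power is 81.5%.

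The stated figure is therefore reproduced within about 2 points. It says nothing about quality of life but supplies the 78 per arm used below.

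**2. Which items have a pre-operative value?**

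| Item | Table 4 and footnote | Text on timing | Pre-operative value |
|---|---|---|---|
| IPSS quality of life | marked, not exempted | no conflicting statement | yes |
| Disturbance, activity restriction | marked within a pooled row, not exempted | post-operative times only | unresolved |
| Return to work, usual activities | exempted | post-operative times only | no |

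The row's item count does not settle the middle line. The IIQ-SF has 7 items, the IPSS question is 1 and the other questions are 4, giving 12. Without the two return items the count is 10. The row says 11.

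**3. Gain for the IPSS question.** Assumptions: linear adjustment of the score, 78 men per arm with data, two-sided 0.05. The documents give no r and no standard deviation, so r is shown as a range.

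- Variance factor = 1 − r².
- Standardised difference with 80% unadjusted power: (1.960 + 0.842) × √(2/78) = 0.449.
- Adjusted power = Φ[2.802/√(1 − r²) − 1.960].

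| Assumed r | Variance factor | Power | Equivalent unadjusted N = 156/(1 − r²) |
|---|---|---|---|
| 0.1 | 0.99 | 80.4% | 158 |
| 0.2 | 0.96 | 81.6% | 163 |
| 0.3 | 0.91 | 83.6% | 171 |
| 0.5 | 0.75 | 89.9% | 208 |

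The variance factor does not depend on the significance level or on sidedness. Any gain from age, Gleason score and site comes on top and cannot be sized from the documents.

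**4. Gain for the two leakage items, if they are asked before surgery.** Eligibility allows "no more than 2 incontinence episodes in the last 6 months, not including post-void dribbling", so most pre-operative answers will sit near the floor. Treat the baseline as yes/no with prevalence p from 7% (2 of 30 in the clinic-based pilot) to 14% ("we would expect about 14% of potential participants to have any pre-existing incontinence, 10% with minor leakage"). Take the outcome as present in a share q from 35% to 55% (the sample-size rates), and assume an odds ratio of 2 to 3 between the two. With m₀ and m₁ the outcome risks without and with baseline leakage:

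- correlation = (m₁ − m₀) × √[p(1 − p)/(q(1 − q))].
- Highest case (p = 0.14, q = 0.35, odds ratio 3): 0.2645 × 0.7275 = 0.192, a variance reduction of 3.7%.
- Lowest case (p = 0.07, q = 0.55, odds ratio 2): 0.083, a variance reduction of 0.7%.

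The gain is thus roughly 1% to 4%.

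**The case against.** The strongest reply is that nothing is broken. Unadjusted tests after stratified, blocked randomisation are valid, chance imbalance is not bias, and this is one secondary outcome. All of that stands.

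It can also be said that r may be low, because men with more than minimal incontinence are excluded. That stands for questions about leakage. It is weaker for the IPSS item, which asks about the urinary problem in general, but the documents contain no data on how much pre-operative answers vary or how well they predict later ones. Nothing in them favours r = 0.5 over r = 0.2.

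The plan also says that stratification serves only to balance the groups and not to compare them. Entering the factors as covariates does not conflict with this, since it makes no comparison between strata.

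A reader might go further in three ways that the documents do not support:

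- **That the IIQ is also compared by unadjusted tests.** The analysis text assigns no test to the IIQ at all. That is a gap in specification and a separate matter.
- **That power is lost by spreading the seven ordered IPSS answers over a chi-square test with six degrees of freedom.** The plan names the t test as well, which has one degree of freedom and uses the order. What can fairly be said is that the plan does not match tests to items.
- **That the variance figures hold for any adjusted model.** The factor 1 − r² belongs to linear regression. In proportional-odds regression, adding a prognostic covariate need not narrow the interval for the log odds ratio, and the effect becomes a conditional one.

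**Conclusion.** The point holds for the IPSS quality-of-life question, as a minor and free improvement. A pre-operative score is scheduled and not used, and the randomisation factors are left out. The variance reduction is 4%, 9% or 25% if r is 0.2, 0.3 or 0.5, taking 80% power to about 82%, 84% or 90%. These figures rest on an assumed r, linear adjustment and complete data on 156 men.

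For disturbance and activity restriction the point is conditional on confirming that they are asked before surgery, and the likely gain is small. For return to work and usual activities nothing is lost, because no pre-operative value can exist. It would be wrong to infer that the planned comparisons are biased or invalid.

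**What to change.** Replace the IPSS part of the sentence in Outcome Variables Analysis with:

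> The IPSS QoL score at 6 and 12 months will be analysed by multiple regression on treatment group, adjusting for the pre-operative IPSS QoL score and the randomisation factors (age <65/65+, Gleason <7/7+, site).

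This follows the regression at 6 and 12 months that the plan already uses for other secondary scores, and the treatment effect remains a difference in means, as with the t test. Because the present sentence names no time point, the new wording adds one. Table 4's separate six-month cell for this row appears to be blank, so the text should say that the six-month value is the last monthly one.

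The covariate must be the pre-operative score. The post-catheter-removal score used as baseline for ICIQ-SF and EPIC-UI should not be copied here: it is measured after randomisation and after pre-operative training has begun, so it may already carry part of the treatment effect.

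Reconcile Table 4 with the timing given for the other quality-of-life questions. If disturbance and activity restriction are confirmed as collected before surgery, apply the same pre-operative adjustment to them. Leave return to work and usual activities without a baseline term.

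For the IPSS question the cost is analysis-plan wording only, with no new data, visits or participants.

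### Return to usual activities is asked eight times, but the planned test names no month and does not use how soon men returned

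*Combined protocol and SAP*

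**What the plan says.** All references are to the combined protocol and SAP.

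- **Item.** Under Secondary Outcome Measures, Other Quality of Life Questions, the item is "Have you been able to resume your usual activities since your surgery? (yes, no", a two-level answer. Its companion is "Have you been able to return to work since your surgery? (yes, no, retired or disabled", which has a third category for men outside the workforce.
- **Schedule.** The same section asks these questions "each month 1-6 months post-operatively and again at 9 & 12 months post-operatively", which makes eight occasions.
- **Baseline.** The footnote to Table 4 lists measures that cannot be taken before surgery and adds "Same with return to work after surgery and return to usual activities after surgery (other QoL items".
- **Hypothesis.** In Data Analysis, Outcome Variables Analysis, the secondary hypothesis is that "IPSS QoL, return to work or normal activity, and amount of disturbance caused by incontinence will be better in the pelvic floor muscle rehabilitation group".
- **Test.** The closing sentence of the same section covers the IPSS quality-of-life question, activity restriction, disturbance and the return items together: "return to work or normal activity, the chi square statistic and the t test for independent samples will be used". No month is attached. The sentence for the global ratings, by contrast, does name its times: "Multiple regression will be used for the GPI, EPI, and PSQ at 6 and 12 months".
- **Methods for timing.** Kaplan-Meier and the log-rank test are planned in that section for time to continence only.

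**The concern.** An item worded as having happened since surgery, with no baseline value and repeated on a fixed schedule, is naturally read as a grouped time to event. A chi-square at one month compares only the proportion who have returned by then. It cannot tell a man who resumed activities at month 1 from one who resumed at month 5 if the test is made at month 6.

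Two things are at stake. First, with eight possible months and none named, the comparison can be chosen after the results are known, or made eight times. Second, if the programme speeds return, information that would help to show it is collected and then left out of the test. The t test adds a smaller problem: the sentence does not say which test belongs to which item, and a t test does not suit a yes/no answer.

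**Working it through.** **1. The plan's own figures.** The documents state no return rate, effect or power for this item. The only power statement is for the primary outcome (Sample size).
- Hazard ratio: ln(0.35)/ln(0.55) = 1.756, as stated.
- Expected events: 156 × (0.45 + 0.65)/2 = 85.8.
- Freedman power, one-sided 0.05: z = √85.8 × (0.756/2.756) − 1.645 = 0.896, giving 81.5% against the stated 80%.

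The primary figure is sound. Only the arm size (78) and, as a borrowed value, 1.756 are carried forward.

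**2. Assumptions.** Exponential time to return, 78 men per arm, complete answers at months 1-6, 9 and 12, no reversal of a yes, two-sided 5%. The proportion of controls returned by month 6 is varied because no source for it exists in the documents.

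**3. Tests compared.**
- *Log-rank on month of first yes.* At visit j, with n₁ⱼ and n₂ⱼ men at risk, nⱼ = n₁ⱼ + n₂ⱼ, and dⱼ first yes answers (d₁ⱼ in arm 1): eⱼ = dⱼn₁ⱼ/nⱼ, vⱼ = dⱼ(n₁ⱼ/nⱼ)(n₂ⱼ/nⱼ)(nⱼ − dⱼ)/(nⱼ − 1), Z = Σ(d₁ⱼ − eⱼ)/√Σvⱼ.
- *Chi-square at one month*, without continuity correction. With control proportion p, the other arm has 1 − (1 − p)^ratio.

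Hand check of one cell (ratio 1.5, month 6, controls 65%): 1 − 0.35^1.5 = 0.793; pooled p = 0.7215; pooled SE = √(2 × 0.7215 × 0.2785/78) = 0.0718; unpooled SE = √[(0.65 × 0.35 + 0.793 × 0.207)/78] = 0.0709; power = Φ[(0.143 − 1.96 × 0.0718)/0.0709] ≈ 51%. Simulation gives 52%.

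**4. Power, rate ratio 1.5 (8,000 simulated trials per row).**

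| Controls returned by month 6 | Log-rank | Chi-square month 3 | Month 6 | Month 12 |
|---|---|---|---|---|
| 65% | 68% | 39% | 52% | 47% |
| 80% | 69% | 48% | 51% | 22% |
| 90% | 69% | 52% | 42% | 1% |
| 95% | 68% | 52% | 27% | 0% |
| 98% | 67% | 47% | 6% | 0% |

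With no effect, the log-rank test rejected in 4.9-5.6% of trials. Over a wider range of control medians (1 to 8 months) its power was about 58-69%, lowest when return is slowest. Chi-square at month 3, 6 or 12 did not exceed about 53%.

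At ratio 1.756 over the same five rows, log-rank has 92-93%; chi-square has 67-81% at month 3, 6-80% at month 6 and 0-69% at month 12.

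**5. Testing every month.** Eight uncorrected chi-square tests give 19-25% false positives under no effect. With a Bonferroni correction, power at ratio 1.5 is 38-48%.

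**6. A pattern that favours the late proportion.** Suppose both arms return at the same speed (median 2 months among returners) but 70% against 88% ever return. Chi-square at month 12 then has about 78% power and log-rank about 71%. With 75% against 90% the figures are 68% and 58%.

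**The case against.** The strongest case against is that the log-rank advantage comes from assuming proportional hazards. Step 6 shows the order reversing when the arms differ only in how many men eventually return. With an effect that starts only after month 2 (rate ratio 2, control median 4 months), the two tests are about level: 75% for chi-square at month 12 and 76% for log-rank. Neither pattern is documented. This stands, and is why one fixed-month proportion should be kept.

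Four stronger readings might be inferred, and the documents do not support them:

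- *That the test will see only a late, near-ceiling proportion.* No month is named; 6 and 12 months belong to the regressions for other outcomes. No return rate appears anywhere.
- *That a real speeding of return would probably be reported as no difference.* This depends on the setting. Under the same model, chi-square at 6 months has 52% power with a control median of 3 months and ratio 1.5, and 71% with a median of 2 months and ratio 1.756.
- *That sooner return to activities is a stated aim.* The Specific Aims and Overview speak of time to continence, which already has a log-rank test. For this item the hypothesis says only that it will be better.
- *That a yes can never revert.* The wording suggests a cumulative status, but a man could answer for his present state.

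The only level the plan states is one-sided 0.05, for the primary outcome. At that level the 6-month chi-square has 50-65% power at ratio 1.5 (control medians of 1.5 to 3 months). The log-rank power rises as well, so the sidedness does not account for the gap. The missing month also affects the other items in the same sentence.

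**Conclusion.** The point holds as a gap in specification and a loss of information. The month is unspecified, the eight answers are not combined, and time to return is not analysed. These three facts need no assumption.

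The size of the loss does need assumptions. Under proportional hazards at ratio 1.5, it is roughly 58-69% power against at most about 53% at months 3, 6 or 12. Power near zero arises only when the test is late and nearly every man has returned. If the arms differ in eventual return rather than in speed, a late proportion can do somewhat better.

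This is a cheap and worthwhile improvement to a secondary outcome. The primary analysis and N = 156 are not affected.

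**What to change.** In Data Analysis, Outcome Variables Analysis, replace the provision for the return items with the following:

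- For usual activities, analyse time from surgery to the first yes, grouped at the scheduled months, with Kaplan-Meier curves and a log-rank test or a discrete-time hazard model. Censor men with no yes at their last answer.
- State how a skipped month and a later no are handled.
- Keep the proportion returned at one prespecified month as a supportive comparison. Show the other months descriptively.
- Drop the t test for this yes/no item.
- Treat return to work in the same way, only among men who are not retired or disabled.

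The cost is a few sentences, written before the outcome data are examined by arm. The data are already collected and the methods are already in the plan for the primary outcome. The downside is the somewhat lower power of the log-rank test if the arms differ only in how many men eventually return; the supportive proportion covers that case.
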